6. BIOSTATISTICAL ANALYSIS

6.1. Statistical analysis will be performed via a mixed model for repeated measures, with Drug (OXT vs. PLA) as a Class factor, psychometric scores as univariate and/or simultaneous multivariate dependent measures, additional covariates as appropriate, and Sbj as a random effect. Currently available mixed model analytic programs are able to handle missing data. Effect sizes will be employed in power analyses to calculate sample sizes for subsequent larger studies. Path analysis will be employed to test the role of bonding as a mediating factor of drug effect on depression outcome.

6.2. Power analysis. The major goal of this first study is to obtain measures of effect size that can be used to calculate sample size requirements for a subsequent, larger study, should the data from this study be promising. Thus, even if we are unable to meet the recruitment goals below, the study will still obtain useful and important data. That being said, we offer the following power analysis below, should recruitment go as well as hoped.

Because of the novelty of this project's hypothesis, no data are available regarding the potential protective effect of IN-OXT against the development of PPD, from which to estimate an effect size for the proposed study. However, a meta-analysis of studies of the effect of intranasal OXT in both healthy and clinical groups with implications for pharmacotherapy yielded an estimated effect size of $d=0.32$ (Bakermans-Kranenburg and van IJzendoorn, 2013), on which we will base our power analysis. With α set at 0.05, and $1-\beta$ (i.e., power) set at 0.80, $n=56$ Sbjs (approximately 28 completed Sbjs in each of two groups) will be required to detect an effect size of $d=0.32$ in a simple t-test analysis comparing OXT and PLA subjects. Estimating dropouts at 20% between assessments, 70 and 88 Sbjs and partners will have to complete the second and first postpartum assessments, respectively, and 110 Sbjs will be required to complete the pre-partum assessment. Of all pre-partum women given psychometrics, an estimated 20% will be found to be at-risk, requiring the administration of psychometrics to 550 study candidates. To summarize:

550 administered psychometrics

110 women identified at risk, pass final screening, and complete pre-partum assessment
88 women randomized, and complete assessment #2; 88 partners complete assessment #1 at day 1 postpartum
70 women complete assessment #3; 70 partners complete assessment #2 at day 5 postpartum
56 women complete participation; 56 partners complete participation

6.3. Successful results.

As above, successful results will consist of our obtaining sufficient data that, if promising, will allow planning of a further, more definitive study of the effective role of IN-OXT in enhancing maternal bonding and/or preventing postpartum depressive and or posttraumatic symptoms, including calculating sample size requirements. Successful results also pertain to gaining knowledge about the potential positive effects of IN-OXT on mother at risk and knowledge about the feasibility of the intervention. Given the under-researched area of PP-PTSD, successful findings will include knowledge about the prevalence, course and risk factors of posttraumatic stress and its relations with depressive symptoms and mother-infant bonding.

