3. SUBJECT SELECTION

For Oxytocin study

3.1. Inclusion Criteria. 1) Third-trimester pregnant women being followed at the MGH Obstetrics Program who are at risk of PPD as indicated by their scoring >9 on a prenatal administration of the Edinburgh Postnatal Depression Scale (EPDS). (Note: Although the adjective “Postnatal” refers to the use of the EPDS during the *postpartum* period, this instrument is also used as a *prepartum* screening instrument for PPD risk.) Additionally, we will enroll women with score of >21 on the Peritraumatic Distress Inventory (PDI) who might also be at risk for bonding impairment from PPD and PP-PTSD.

3.2. Exclusion criteria. 1) Age <18 or >50; 2) Failure to participate in regular prenatal check-ups; 3) Current diagnosis of psychosis; 4) Obstetric complication (e.g., preeclampsia, excessive hemorrhaging, gestational diabetes insipidus, emergency Caesarian section resulting in the newborn being admitted to the NICU). Note that planned Caesarian section will not serve as an exclusion criterion because immediate contact with the newborn occurs after the procedure.); 5) Use of potentially confounding or interacting medications (e.g. antidiuretic hormone, steroids); 6) Complicating pediatric medical condition in the newborn.; 7) suicidality (candidates indicating 2+ on EPDS item 10 will be further assessed by PI, a licensed clinical psychologist); 8) current substance abuse.

3.3. Recruitment methods. 3596 women delivered a baby at Massachusetts General Hospital (MGH) in 2012. During proposed five-year project period, we plan to recruit 110 subjects (Sbj's) (who satisfy the inclusion and exclusion criteria) and expect a drop-out rate of 20% between assessments, resulting in an anticipated final sample of 56 women. Additionally, we plan to recruit and study 88 partners (starting at day 1 postpartum, taking into account women's drop-out rate between pre-partum and day 1 postpartum assessments), also expecting a drop-out rate of 20% between assessments, resulting in a final sample of 56 partners.

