NCT02505984

Preventing Postpartum Depression with Intranasal Oxytocin

Date of document: 12/27/2024

Data Analysis

The final sample size includes 38 eligible women randomly assigned to oxytocin administration ($n = 18$) or placebo ($n = 20$). Missing data were allowed such that 18.59% of the data were missing, with 23 different patterns. Jamshidian and Jalal's non-parametric Missing Completely At Random (MCAR) test indicated that the data was Missing At Random (MAR): Hawkins's test, $\chi^2_{\text{median}(6)} = 14.33$, $p_{\text{median}} = .026$, and Anderson-Darlin's rank test, $T_{\text{median}} = 5.88$, $p_{\text{median}} = .005$. Missing data was handled by Multiple Imputation (Rubin, 2009) with 50 complete sets. The reported basic results are the pooled outcome of the MI procedure. Before the primary analyses, we examined the normal distribution of all the quantitative study measures using a series of Anderson-Darling normality tests. Basic analyses for study group comparison on outcome measures for each time point were performed using Mann-Whitney U tests.

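### Section 6.2 claims 80% power for d=0.32 with 28 women per group; the t-test it names has about 22% (32% one-sided) and would need about 155 (122) per group

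*Protocol*

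**What the plan says.** Section 6.2 of the protocol opens with the purpose of the study: "The major goal of this first study is to obtain measures of effect size that can be used to calculate sample size requirements". It adds that the data will be useful even if recruitment falls short, and then offers a power analysis. The inputs are d=0.32, taken from a meta-analysis of intranasal oxytocin studies, and "With α set at 0.05, and $1-\beta$ (i.e., power) set at 0.80". The result is 56 completers: "approximately 28 completed Sbjs in each of two groups) will be required to detect an effect size of $d=0.32$ in a simple t-test analysis". Sidedness is not given.

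The rest of the recruitment plan is worked backwards from 56, using 20% dropout between assessments and a 20% at-risk rate. It gives 70 women at the day 5 assessment, 88 randomised, 110 at the pre-partum assessment, and ends by "requiring the administration of psychometrics to 550 study candidates". Section 3.3 repeats the target: "resulting in an anticipated final sample of 56 women".

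The SAP makes no power statement. It reports the achieved size, "The final sample size includes 38 eligible women randomly assigned to oxytocin administration" (18, against 20 on placebo), and describes the group comparison: "Basic analyses for study group comparison on outcome measures for each time point were performed using Mann-Whitney U tests".

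**The concern.** A standardised difference of 0.32 is small, and 28 per group is far too few to detect it with 80% power in a plain two-group comparison. The gap is too wide for rounding or the missing sidedness to explain.

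This is the only sample-size justification in either document. Taken at face value, it tells a reader that full recruitment would have given a fair test of d=0.32. A non-significant result could then be read as evidence against that effect, or blamed only on the shortfall in recruitment. Neither reading would be sound. It also gives a misleading idea of how precise the effect-size estimate would be, and that estimate is what the study says it is for.

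**Working it through.** **Inputs, all from section 6.2:** d=0.32; alpha 0.05; power 0.80; independent two-group t-test; 56 completers, 28 per group. Sidedness is not stated, so both versions are computed.

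**1. Can the 56 be reproduced?** The normal approximation is n per group = 2(z for alpha + z for power)² / d², with d² = 0.1024.

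- Two-sided: 2 × (1.960 + 0.842)² / 0.1024 = 2 × 7.849 / 0.1024 = 153.3, so 154.
- One-sided: 2 × (1.645 + 0.842)² / 0.1024 = 2 × 6.183 / 0.1024 = 120.8, so 121.

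The exact noncentral-t calculation gives 154.3 and 121.4, so **155 per group (310) two-sided or 122 per group (244) one-sided**. The stated 28 is too small by a factor of 155/28 = 5.5 or 122/28 = 4.4.

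**2. Power at the stated size.** The noncentrality parameter is d × √(n1·n2/(n1+n2)). At 28/28 it is 0.32 × √14 = 1.197, on 54 degrees of freedom, against a critical value of 2.005 two-sided or 1.674 one-sided. Other sizes follow the same way.

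| Sample | Power, two-sided | Power, one-sided |
|---|---|---|
| 28/28 (56 completers) | 21.7% | 32.2% |
| 35/35 (70 at day 5) | 26% | 37% |
| 44/44 (88 randomised) | 32% | 44% |
| 18/20 (SAP) | 16% | 25% |

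The effect detectable with 80% power is d = 0.76 (0.67 one-sided) at 28/28 and 0.94 (0.82) at 18/20.

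**3. Other readings.** A paired or one-sample t-test with d=0.32 needs 79 (62 one-sided), and would not fit a comparison of two groups. Two different calculations do land on 56. One reads 0.32 as a correlation (equivalent d = 0.676) and tests it one-sided, giving 27.8 per group. The other is a group-by-time F-test over four occasions with f=0.16 and correlation 0.5, with power 0.811 at N=56. Neither is a simple t-test with d=0.32, and the documents do not show where the figure came from.

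**4. The recruitment chain.** From 56 it is consistent: 56/0.8 = 70; 70/0.8 = 87.5, so 88; 88/0.8 = 110; 110/0.2 = 550. The fault is in the starting number. From 310 completers the same steps give 310/0.8 = 388, 388/0.8 = 485, 485/0.8 = 606 and 606/0.2 = 3,030 (607 and 3,035 if rounded up).

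**5. Precision.** The large-sample standard error of d is √[(n1+n2)/(n1·n2) + d²/(2(n1+n2))].

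- At 28/28: √(0.07143 + 0.00091) = 0.269. The half-width is 1.96 × 0.269 = 0.527, so an observed 0.32 has a 95% interval of about -0.21 to 0.85.
- At 18/20: √(0.10556 + 0.00135) = 0.327. The half-width is 0.641, and the interval is about -0.32 to 0.96.

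**6. The SAP's test.** Simulating a two-sided Mann-Whitney test on complete normal data (100,000 runs) gives 15% power for d=0.32 at 18/20, with 80% power reached at d of about 0.97. At 28/28 the figures are 20% and about 0.79. The imputation of the 18.59% missing data is not modelled.

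**The case against.** The strongest reply is that this is an estimation study. Section 6.2 says so before it gives any power figure and presents the calculation as conditional on good recruitment. Section 6.3 defines success as data for planning a later trial. No decision rule depends on 80% power, and neither document says that a non-significant result will count against d=0.32. All of that is correct, and it limits the harm. It does not rescue the sentence, which still states a required number for a named test, effect and power, and that number is false.

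A second reply is that section 6.1 plans a mixed model, which can be more efficient than a t-test. But section 6.2 rests its figure on the t-test, and the documents give no correlation between visits. As an illustration, assume the mean of two post-dose visits, adjusted for baseline, with equal correlations rho and d=0.32 at both visits. The variance factor is then (1+rho)/2 - rho². Two-sided power at 28/28 is 35%, 38%, 50% and 64% for rho of 0.3, 0.5, 0.7 and 0.8, all below 80%. With all 88 women and no dropout it is 51%, 56%, 70% and 83%. These figures suit only measures taken on day 1, day 5 and at two months, such as the EPDS and MIBS. They do not apply to the PBQ (first given at day 5), the MAI (day 5 only) or the coded video (two months only).

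Third, power at the achieved 18 and 20 is after the fact, and the SAP claims none. That is fair. Confidence intervals convey the imprecision better, and the power figures for 38 women serve only as context.

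**Conclusion.** The concern holds. As written, section 6.2 overstates power for d=0.32: about 22% two-sided or 32% one-sided, not 80%. The conclusion does not depend on the missing sidedness, because both versions fail by a wide margin. It uses only the protocol's own inputs and the usual t-test assumptions. If the true d is 0.32, the two-sided test at 28 per group would be non-significant about 78% of the time (100 - 22), so non-significance would say little against that effect.

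Full recruitment would not have given the stated power. The figures for 18 against 20 are complete-data approximations. The mixed-model figures rest on assumed correlations and are illustrative. The correction is compatible with the estimation goal, but it is a necessary one because no other sample-size justification exists.

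**What to change.** In section 6.2, remove the statement that 56 is the number required for d=0.32 and replace it with wording such as:

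> With 28 completers per group, a two-sided t-test at alpha 0.05 has about 22% power for d=0.32 and 80% power for d of about 0.76; d=0.32 would require about 155 per group.

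If one-sided testing was intended, say so and give 32%, 0.67 and 122 per group. Describe 56, and the 70, 88, 110 and 550 derived from it, as feasibility targets for the estimation goal.

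For the SAP's sample, add as context that a complete-data two-sided t-test at 18 against 20 has about 16% power for d=0.32 and 80% for d of about 0.94 (Mann-Whitney about 15% and 0.97), without modelling the multiple imputation. Report effect sizes with 95% confidence intervals, and state that non-significance is not evidence against d=0.32. If mixed-model power is shown, give it as a range over the assumed correlation.

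The cost is wording only, with no extra participants and no change of design. The price is a less favourable power statement.

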7. RISKS AND DISCOMFORTS

7.1. Study Medication. OXT nasal spray has been previously administered to women following childbirth. There are reports of mild side effects at a dosage to promote lactation for as early as day 1 postpartum (e.g., Fewtrell et al., 2006; Ruis et al., 1981). Mild complaints may include: breast and nipple discomfort (13-20 out of 100) and uterine cramps (5 out of 100). However, such side effects were also reported by women receiving placebo (Stern, 1961). As indicated in the drug brochure, women experiencing painful uterine cramps should not drive or operate machinery. Other uncommon side effects include bleeding from the nose after using the drug (1 out of 48) (Huntingford, 1961), unfamiliar sensation in the nose (5 out of 100), and complaint about taste (1 out of 100) (Stern, 1961). Use of the drug by participants who experience postpartum depression was reported to transiently lower mood (Mah et al., 2013). A subsequent study, however, by the same group did not mention these outcomes (Mah et al., 2015), nor were these outcomes reported elsewhere (Clarici et al., 2015). A recent study by Mah and colleagues (2017), based on the 2013 sample, reports no effect of IN-OXT on maternal sensitive interaction with own baby but more negative care giving response to another's baby. The authors warrant further research on IN-OXT in depressed mothers. Other potential undesirable effects mentioned in the nasal spray package insert but not encountered in the literature include: headache, nausea, rash and allergic dermatitis (all rare).

7.2. Questionnaires and video recording. Sbj may experience emotional distress from answering questions concerning their mental health and childbirth experience. Interacting with their infant on camera may cause Sbj discomfort.

7.3. Blood drawn. Sbj may experience discomfort from having blood drawn. Side effects may include bruising, swelling at the injection site, dizziness and lightheadedness.

7.4. Unknown Risks. There may be other risks and side effects that are not known at this time. If any significant new findings develop during the course of this study that may affect the risk: benefit ratio for participants, appropriate institutional reporting protocol will be followed.

8. POTENTIAL BENEFITS

8.1. Potential benefits to participating individuals. First, women with PPD have an increased incidence of lactation problems (Assarian et al., 2014), and they are at risk for breastfeeding failure and cessation (see Figueiredo et al., 2013, for a review). This can be unfortunate, because breastfeeding helps to reduce PPD symptoms (Fairlie et al., 2009; Figueiredo et al., 2014; Ystrom, 2012). Therefore, it is reasonable to expect that a significant portion of our Sbjs (and their newborns) who receive active drug will benefit from the lactation-promoting effect of IN-OXT, with consequent benefit to infant nutrition and reduction in maternal anxiety. Second, in a recent study of women with PPD three months following delivery (Mah et al., 2015), IN-OXT was found to enhance the quality of mother-infant bonding and maternal protective behavior. Hence, our proposed active intervention may benefit the newborn as well. Third, women who receive active drug may be protected from developing PPD and bonding impairment. Other less substantive benefits include, if this turns out to be the case, the use of IN-OXT may reduce or obviate the need for antidepressant medication, with a reduction of possible transmission via secretion into maternal milk. Further, PPD is often accompanied by symptoms of anxiety and irritability (Righetti-Veltema et al., 2003). OXT has been shown to attenuate the neural response to arousing stimuli (Rupp et al., 2013) and to reduce amygdala activation in response to infant crying (Riem et al., 2011). Thus we have reason to expect that OXT may prevent to some degree PP-PTSD symptoms in women at risk.

8.2. Potential benefits to society. The information collected from this study may enable researchers to obtain knowledge on the effectiveness of oxytocin for enhancing bonding and preventing depressive and posttraumatic symptoms in postpartum women. If the findings are promising, this study may serve as a platform for larger-scale studies that may ultimately support a new drug indication for postpartum women at risk.

9. MONITORING AND QUALITY ASSURANCE

9.1. Administration of Protocol.

The protocol will be conducted in accordance with the protocol submitted to and approved by the Partners MGH IRB, as well as by NARSAD and ECOR. Sbjs will not be recruited until written notification of approval of the research project is issued by the IRB and NARSAD and ECOR are notified of the approval.

9.2. Data Monitoring. Given the reduced risk of this study, monitoring by the PI and Partners IRB should be sufficient. A physician investigator will review all laboratory/questionnaire results. The PI will closely monitor emotional dysregulation and concerning responses to questionnaire items that inquire about suicidality (BSI, question #9, responses of 2 or more; EPDS question #10, responses of “sometimes” or “yes, quite often”). Women who report suicidality in the screening and consent to the study will be monitored by the PI during their study participation. Likewise, the PI will monitor subjects who report suicidality in subsequent study assessments. If needed, the PI will conduct a suicidality assessment. Based on Sbj’s response, several actions will take place, including frequent contact with Sbj during study participation, suicide contract, referral for psychiatric consultation and treatment for medication,

if needed, and, in extreme cases, hospitalization. PI, who is a licensed clinical psychologist, will immediately evaluate subject suicide-related responses as data becomes available and will immediate attempt to contact subject for assessment and appropriate triage. The PI will review cases that are clinically significant and will notify the IRB in case of adverse events that may influence the IRB decision to continue or not the study trials, in accordance with IRB's policies. In the event possible serious or adverse effects of participation, [name]., an MGH psychiatrist who has served as a Medical Monitor on other studies conducted by the MGH PTSD group, and who is not an investigator on the present study, will be available to review the event and make recommendations to the PI and the IRB.

9.3. Communication between Principal Investigator and Sponsor. The PI will provide written reports about the study progress to NARSAD. Six months after the project start date, the PI will send an interim report followed by a second report one year later. A final report will be sent within 90 days of the grant termination. The final report will include a narrative pertaining to the main findings of the study and information about additional grants, if relevant. NARSAD will also obtain from the PI copies of relevant presentations and publications generated by the study. Additionally, annual and final progress report will be submitted to NIH. If any change is considered in the protocol, an amendment will first be sent to the IRB, and significant changes in the protocol will be sent to NARSAD for review and approval. We will notify the FDA of significant changes to the protocol and we will send a report to the FDA of adverse events that are serious, related, and unexpected within 90 days.

NCT02505984

Preventing Postpartum Depression with Intranasal Oxytocin

Date of document: 12/27/2024

Data Analysis

The final sample size includes 38 eligible women randomly assigned to oxytocin administration ($n = 18$) or placebo ($n = 20$). Missing data were allowed such that 18.59% of the data were missing, with 23 different patterns. Jamshidian and Jalal's non-parametric Missing Completely At Random (MCAR) test indicated that the data was Missing At Random (MAR): Hawkins's test, $\chi^2_{\text{median}(6)} = 14.33$, $p_{\text{median}} = .026$, and Anderson-Darlin's rank test, $T_{\text{median}} = 5.88$, $p_{\text{median}} = .005$. Missing data was handled by Multiple Imputation (Rubin, 2009) with 50 complete sets. The reported basic results are the pooled outcome of the MI procedure. Before the primary analyses, we examined the normal distribution of all the quantitative study measures using a series of Anderson-Darling normality tests. Basic analyses for study group comparison on outcome measures for each time point were performed using Mann-Whitney U tests.

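### The SAP treats evidence against MCAR as proof of MAR; the multiple-imputation results rest on an untested assumption, and neither document describes a check against departures from it

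*SAP*

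**What the plan says.** The SAP's Data Analysis section describes 38 randomized women, 18 on oxytocin and 20 on placebo. On missing data it states: "Missing data were allowed such that 18.59% of the data were missing, with 23 different patterns". It then reports that a non-parametric "Missing Completely At Random (MCAR) test indicated that the data was Missing At Random (MAR", citing Hawkins's test (chi-square 14.33 on 6 df, median p = .026) and an Anderson-Darling rank test (T = 5.88, median p = .005).

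Multiple imputation with 50 sets follows, and "The reported basic results are the pooled outcome of the MI procedure". The arms are compared by rank test: "Basic analyses for study group comparison on outcome measures for each time point were performed using Mann-Whitney U tests". The SAP also refers to a further set of analyses, "Before the primary analyses, we examined the normal distribution of all the quantitative study measures", but does not describe them.

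Protocol section 6.1 plans a mixed model for repeated measures. Its only remark on missing data is "Currently available mixed model analytic programs are able to handle missing data". Section 6.2 gives the purpose of the trial: "The major goal of this first study is to obtain measures of effect size that can be used to calculate sample size requirements".

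**The concern.** A small p-value from an MCAR test is evidence against MCAR. It does not choose between the two alternatives that remain. Under MAR, missingness depends only on what was observed; under MNAR, it also depends on the values that were not seen. The observed data carry no information on that difference. The SAP therefore reports as a test result something that no test of these data could show.

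The sentence matters because the analysis builds on it. A reader who believes that MAR was established will see no need for a sensitivity analysis, and neither document describes one. There is no delta adjustment, pattern-mixture or tipping-point analysis, and no complete-case comparison. A likelihood-based mixed model also relies on MAR, so agreement between it and the imputed results would not check the assumption.

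What is at stake is the effect size that the trial is meant to supply for planning a larger study. Most outcomes are self-reported mood, bonding and trauma symptoms, so non-response related to the unseen score is possible, though not shown. The single overall percentage does not tell a reader how much is missing at 2 months or whether the arms differ.

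**Working it through.** **1. The SAP's own figure.** The upper tail of chi-square at 14.33 on 6 df is 0.0262, so the quoted .026 reproduces. The rank-test p of .005 cannot be recomputed without the data. The arithmetic is sound; the inference is the error.

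**2. Rejection occurs under both mechanisms.** This was simulated with assumed settings: 38 women, within-subject correlation 0.6, logistic missingness of about 15% to 19%, 4,000 runs. A simple t-test of whether the earlier score differs by missingness stood in for the SAP's tests. It rejected MCAR in 82% of runs under MAR, 37% under MNAR in both arms, and 14% under MNAR in one arm. The rates depend on the settings; the logical point does not.

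**3. Inputs for an illustration of size.**
- Arm sizes 18 and 20 (SAP).
- Effect d = 0.32 (protocol 6.2). This is a planning value from a meta-analysis, not a trial result.
- Fraction missing m, assumed equal in both arms because it is not given by arm or time point. Case A uses the SAP's overall m = 0.1859. Case B uses the protocol's planned attrition from "88 women randomized, and complete assessment #2" to 56 completing: m = 1 − 56/88 = 0.364.
- Scores normal with equal variance (assumption).

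**4. Movement of the mean difference.** Shifting the imputed values in one arm by δ SD moves the difference by m × δ. For δ = 0.5 to 1:
- A: 0.1859 × 0.5 = 0.09 to 0.1859 × 1 = 0.19 SD.
- B: 0.364 × 0.5 = 0.18 to 0.364 × 1 = 0.36 SD.

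Equal shifts in both arms with equal missingness cancel to 0.

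**5. Shift that removes d = 0.32.** One arm: δ = d/m. Opposite directions in the two arms: δ = d/(2m).
- A: 0.32/0.1859 = 1.72 SD; opposite directions 0.86 SD.
- B: 0.32/0.364 = 0.88 SD; opposite directions 0.44 SD.

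**6. Compared with sampling error.** With full data, SE = √(1/18 + 1/20) = 0.325. With complete cases only, SE = 0.325/√(1 − m), which is 0.360 in A and 0.407 in B. Imputation may recover some information, so the relevant value lies between. A 1 SD one-arm shift is then:
- A: 0.186/0.360 = 0.52 to 0.186/0.325 = 0.57 SE.
- B: 0.364/0.407 = 0.89 to 0.364/0.325 = 1.12 SE.

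Even with full data, the approximate 95% interval around d = 0.32 is 0.32 ± 1.96 × 0.325 = −0.32 to 0.96.

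**7. The crossing point depends on the estimate.** The SAP uses Mann-Whitney tests. On that scale, the one-arm shift x that removes the effect solves (1 − m)Φ(d/√2) + mΦ((d − x)/√2) = 0.5. At m = 0.1859:

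| d | x (SD) |
|---|---|
| 0.1 | 0.54 |
| 0.2 | 1.14 |
| 0.32 | 2.07 |
| 0.4 | 3.58 |
| 0.5 | none |

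At d = 0.5 the observed part alone gives 0.8141 × Φ(0.354) = 0.520, above 0.5, so no one-arm shift crosses. No fixed SD range suits every result.

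**The case against.** The best reply is that this is a wording error with little practical effect. Multiple imputation under assumed MAR is a standard choice, and no number in the SAP changes when the sentence is corrected. In case A, sampling error is larger than the movement from a 1 SD one-arm shift. Case B applies the protocol's planned attrition to the 38 women whom the SAP calls its final sample, and nothing in the SAP shows that this much is missing. The SAP is one short paragraph, so a check may belong to the primary analyses it leaves undescribed. Missingness by arm and visit is ordinarily a results table.

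Much of this stands. It limits the size of the point and rules out any claim about the follow-on sample size. It does not rescue the inference, and it does not supply a check. That cases A and B differ so much is itself a reason to report the missingness.

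A reader might also infer that the MCAR test was too weak to use because 23 patterns are spread over 38 women. The documents do not support that. The SAP reports 6 df beside 23 patterns without saying which patterns were compared, so the count alone does not show how thin the test was.

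**Conclusion.** The concern holds in a limited form. Reading a rejected MCAR test as showing MAR is wrong. The pooled imputation results rest on MAR as an assumption, and neither document describes a check against departures from it. The same applies to the mixed model of protocol 6.1 if that is what the SAP means by the primary analyses; the SAP does not say.

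A reader might go further and conclude that the data are MNAR, that the effect estimate is biased, or that multiple imputation should not have been used. The documents support none of these. The tests cannot point to MNAR any more than to MAR, and without missingness by arm, outcome and time point neither the direction nor the size of any bias can be determined.

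The sizes are illustrations that assume d = 0.32, equal missingness in the arms and normal, equal-variance scores. On that basis the mean difference is removed by a one-arm shift of about 1.72 SD at 18.59% missing or 0.88 SD at 36.4%. A 1 SD one-arm shift is about 0.5 to 0.6 SE in the first case and 0.9 to 1.1 SE in the second. The correction should be made, but the point does not invalidate the analysis.

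**What to change.** Replace the sentence with: *The tests gave evidence against MCAR; MAR cannot be tested and is assumed.* Report missingness by arm, outcome and time point beside it.

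Add a delta-adjusted analysis, labelled post hoc, of the 2-month depression and bonding outcomes (for example EPDS and MIBS, since the documents name no single primary instrument). Shift the imputed values in the 50 existing sets in each arm separately, in both arms together and in opposite directions. Re-pool, and report the effect estimate across the range. Set the range from the trial's own estimate and missingness, so that it either finds where the conclusion changes or shows that no plausible shift changes it. If the mixed model is the primary analysis, state its MAR assumption and apply the same check.

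The cost is one sentence, one table and a modest extra analysis. The SAP does not list the variables in the imputation model; if arm or earlier scores were left out, adding them means re-imputing. The analysis will be post hoc and imprecise with 38 women.
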